5.1 Timing of Analyses

Statistical analysis will be performed after the last patient has completed the study primary endpoint according to the interim and final analysis plan (see Section 5.7) after the database was checked, cleaned and appropriately locked.

5.2 Analysis Populations

5.2.1 Full Analysis Population (Full Analysis Set)

The Full Analysis Set (FAS) set will be used for all efficacy analyses and is defined as all patients who are randomised to treatment. Patients in this population will be analysed according to the treatment to which they were randomised. All available data for PFS and survival will be collected and analysed for these patients. FAS patients who have inadequate data post-baseline to assess efficacy according to the criteria for response or who dropped out before 30 months follow up (without appropriate PD or death event) will be considered censored for analysis of PFS on the date of the last adequate tumour assessment prior to withdrawal (See Section 3.4.1 for more details).

The confirmatory analysis of the primary and the 2 key secondary endpoints will be based on the FAS.

5.2.2 Per Protocol Population

In order to determine if any bias results from including untreated patients or patients lost to follow-up in the primary FAS analysis, an additional analysis will be conducted on patients who are protocol-compliant: the Per Protocol set (PPS).

The PPS set is defined as:

- All patients with no serious protocol deviation determined before statistical analysis plan finalisation

Serious protocol deviations are defined as those that could impact the efficacy or safety evaluations, as well as data integrity and will be specified in section 6.2, Protocol Section 9.3.3.2 and protocol deviation plan.

5.2.3 Safety Population

Safety Analysis set (SAF)

All patients who received at least one dose of any study treatment will be included in the SAF. Patients will be analysed according to the treatment they actually received. Analyses of safety parameters will be based on the SAF.

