--	--

HPLC and gamma-counting (Sub-study C). In addition, bone marrow dosimetry will be assessed by measuring radioactivity in blood samples taken at pre-defined intervals between end of  $^{177}\text{Lu}$ -edotreotide injection to 7 days post-injection. Sub-study C will be performed during any one of the four  $^{177}\text{Lu}$ -edotreotide treatment cycles (the choice of which of the four cycles to collect urine and blood samples for Sub-study C will be at the investigator's discretion). In order to facilitate the patient recruitment in the regulatory required Sub-study C, [REDACTED] at the sites participating in Sub-study C and only at those sites: Following approval of this Study Protocol Amendment and activation of [REDACTED] by the Sponsor, the patients who consent to participate in Sub-study C and who comply with all protocol inclusion and exclusion criteria will directly be allocated to the PRRT arm until a global cumulative number of 20 evaluable patients is reached for the Sub-study C. [REDACTED] the tests conducted for Sub-study C, the treatment regimen and patient care management will remain identical to that implemented in the main study. [REDACTED]

The patients at Sub-study C participating sites who consent to participate in the main study but not in the Sub-study C, or the patients who are consented and screened out of or after the end [REDACTED] can be randomised in the main study provided they comply with all protocol inclusion and exclusion criteria. The sites not participating in the Sub-study C continue to only enroll patients using the randomization procedure of the main study.

Everolimus: Patients randomised to everolimus therapy will undergo out-patient visits only. Patients will receive a standard dose of 10 mg daily, which may be reduced, where required for acceptable tolerability, according to manufacturer's product information.

For both study arms: Study visits will be monthly in the first 12 months, thereafter 3-monthly until end of study at month 30 or until progression (whatever occurs first). For symptom control, all patients are allowed to receive somatostatin analogues (SSA), as clinically indicated (best supportive care) in required doses, not to exceed licensed doses. In the  $^{177}\text{Lu}$ -edotreotide arm, clinically established wash-out periods prior to  $^{177}\text{Lu}$ -edotreotide dosing have to be considered (1 day for immediate release, and 28 days for sustained release SSA).

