**Table 4: Sampling Schedule Sub-study C**

	Sampling Schedule Sub-study C ‡									
Time Post-injection	Day 0*						Day 1	Day 2	Day 3	Day 7
	0 min	10 min	30 min	1 h	3 h	6h	24±3h	48±3h	72±12h	168±12h
Urine	X †			X		X	X	X		
Blood	X	X	X	X	X	X	X	X	X	X

\* Blood samples can be taken within ± 5 minutes of the scheduled time, as long as the exact sampling times are recorded in the CRF.

† Urine will be collected from all voids beginning immediately at 0 min post-dose into 4 pooled samples in intervals from 0 min post-dose to 1 hour, and 1-6, 6-24 and 24-48 hours post-injection.

‡ Sub-study C will be performed during any one of the four  $^{177}\text{Lu}$ -edotreotide treatment cycles (the choice of which of the four cycles to collect urine and blood samples for Sub-study C will be at the investigator's discretion).

In order to facilitate the patient recruitment in the regulatory required Sub-study C, [REDACTED] at the sites participating in Sub-study C and only at those sites:

Following approval of this Study Protocol Amendment and activation of [REDACTED] by the Sponsor, the patients who consent to participate in Sub-study C and who comply with all

protocol inclusion and exclusion criteria will directly be allocated to the PRRT arm (See Section 3.1) until a global cumulative number of 20 evaluable patients is reached for the Sub-study C.

Aside from this [REDACTED] and the tests conducted for Sub-study C (see above), the treatment regimen and patient care management will remain identical to that implemented in the main study. However, [REDACTED]  
[REDACTED]  
[REDACTED]

After this [REDACTED] Sub-study C cohort is closed or if not activated or during the time this cohort is activated for the patients who consent to participate in the main study but not in the Sub-study C, the patients have the possibility to be randomised in the main study until study termination provided they comply with all protocol inclusion and exclusion criteria.

The sites not participating in the Sub-study C continue to only enroll patients using the randomization procedure of the main study.

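### Once the direct-allocation cohort is activated, never-randomised Sub-study C patients would enter the PRRT column of the safety tables, and the SAP does not say how to separate them

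*SAP*

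**What the plan says.** **Entry route.** The Protocol Synopsis (study design) and Protocol 3.6.3 describe a cohort at Sub-study C sites that opens after the amendment is approved and the sponsor activates it. The route covers "the patients who consent to participate in Sub-study C and who comply with all" eligibility criteria, and they "will directly be allocated to the PRRT arm until a global cumulative number of 20 evaluable patients is reached for the Sub-study C". The target is a worldwide cumulative count of evaluable patients. Patients at the same sites who decline Sub-study C can still be randomised, and sites outside Sub-study C only randomise. Protocol 3.6.3 also provides for the case in which the cohort is never opened: "Sub-study C cohort is closed or if not activated".

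**Analysis sets.** The three SAP definitions treat randomisation differently:
- FAS (SAP 5.2.1): it "is defined as all patients who are randomised to treatment". It serves all efficacy analyses, including the confirmatory ones.
- PPS (SAP 5.2.2): "All patients with no serious protocol deviation determined before statistical analysis plan finalisation". It is introduced as a check on the FAS analysis.
- SAF (SAP 5.2.3): "All patients who received at least one dose of any study treatment will be included in the SAF", analysed by treatment received. Protocol 9.3.3.3 agrees.

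**Safety displays.** SAP 8.1 (adverse events), 8.4 (laboratory) and 8.5 (TER, GFR, renal volume, vital signs, ECG) summarise by treatment arm. None has a separate column for patients who were not randomised. SAP 5.2.4 limits sub-study variables to sub-study participants, but it does not take participants out of any other set.

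**Redaction.** Protocol 3.6.3 says that "patient care management will remain identical to that implemented in the main study. However", and the text that follows is blacked out. Text on this cohort is also blacked out in the Synopsis and in Protocol 4.1.

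**The concern.** A patient on this route receives PRRT because he or she agreed to Sub-study C. Every other PRRT patient has it by 2:1 randomisation. The two groups may differ in site, calendar period and willingness to accept extra blood and urine sampling, and the everolimus column has no group that entered in the same way. If both are pooled under PRRT, the side-by-side safety percentages are no longer a comparison of randomised patients only, and a reader of the tables could not see this.

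The SAP describes only 2:1 randomisation in its design sections (3.1 to 3.3) and does not mention direct allocation. For another group given PRRT outside randomisation, the French rollover patients, SAP 17.5 sets up separate analysis sets. Nothing comparable is visible for the Sub-study C cohort.

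**Working it through.** The plan states no figure on this point, so there is none to reproduce. The check compares definitions and then bounds the size.

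**Step 1: which sets admit a directly allocated, dosed patient?**
- FAS: no, because it requires randomisation.
- SAF: yes, because one dose suffices, and always under PRRT because the set is analysed as treated.
- PPS: unclear. The words cover all patients without a serious deviation, and entering by a route the protocol permits is not among the deviations in SAP 6.2. But SAP 5.2.1 uses the FAS for all efficacy analyses, SAP 5.2.2 presents the PPS as a check on the FAS result, and Protocol 9.3.3.2 forms it by excluding violators. Such a patient also has no randomisation date, which SAP 3.4.1 needs for PFS time zero and SAP 5.6 needs for efficacy baseline. A stratified log-rank test (SAP 7.1) would need a rule for the stratum. These points suggest that a subset of the FAS was meant, though the SAP does not say so.

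**Step 2: share of the PRRT safety column.** Inputs: 200 planned PRRT patients (SAP 3.1) and a ceiling of m = 20 evaluable patients (Protocol 3.6.3). The legible text does not say whether m adds to the 200 or counts within it, so both are shown.

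| Directly allocated, m | Added: m/(200 + m) | Within: m/200 |
|---|---|---|
| 0 (not activated) | 0% | 0% |
| 5 | 5/205 = 2.4% | 2.5% |
| 10 | 10/210 = 4.8% | 5.0% |
| 20 | 20/220 = 9.1% | 10.0% |

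The everolimus share is 0% throughout. If randomised patients who already took part in Sub-study C count toward the 20, m is smaller. Because the ceiling counts evaluable patients, dosed but non-evaluable patients could raise the share slightly.

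**Step 3: effect on a PRRT event percentage.** With share s, event rate r in randomised PRRT patients and rate d in directly allocated ones, the pooled rate is (1 − s)r + sd. It differs from r by s × (d − r). The documents give no value for d − r, so a range is assumed, at the ceiling of 20 patients:

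| Assumed d − r | s = 20/220 | s = 20/200 |
|---|---|---|
| 5 points | 0.45 | 0.50 |
| 10 points | 0.9 | 1.0 |
| 20 points | 1.8 | 2.0 |
| 30 points | 2.7 | 3.0 |

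The last two columns are the shift of the PRRT percentage in percentage points.

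**The case against.** **The redacted text may settle it.** The blacked-out sentences stand exactly where a rule for this cohort would be expected. This stands: no gap can be asserted for the protocol, and actual mixing cannot be confirmed. What remains is that the legible SAP definitions carry no restriction.

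**An all-treated safety set is standard.** It is, and the by-arm safety summaries are counts and percentages, not confirmatory tests. Taking dosed patients out of safety reporting would be worse than pooling them. This also stands, and it is why the SAF itself should be kept. The convention does not, however, explain why patients who were never randomised should be pooled in a by-arm table without being identified. SAP 8.1 allows further tables where appropriate, but it does not commit to one.

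**Stronger readings to avoid.**
- A reader might infer that the PPS analysis of PFS is contaminated. The documents do not show this. The wording is loose, but the purpose of the PPS and the need for a randomisation date point the other way.
- A reader might infer that these patients have no concurrent everolimus patients to be set against. The Synopsis and Protocol 3.6.3 contradict this: patients who decline Sub-study C at the same sites, and patients at all other sites, can be randomised while the cohort is open. What is missing is a randomised counterpart among those who enter by this route.
- A reader might infer that all Sub-study C patients bypass randomisation. The route applies only after activation, which may never have happened.

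**Conclusion.** The point holds as a limited gap in the SAP. If the cohort was activated, the legible SAF definition and the by-arm displays would place up to 9.1% (or 10.0%) never-randomised patients in the PRRT safety column and none in the everolimus column. At that ceiling, assumed rate differences of 5 to 30 points would move a PRRT percentage by about 0.45 to 3.0 points. The direction is unknown.

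This rests on three assumptions: that the cohort was opened, that most of the 20 came through it, and that no redacted sentence already separates them. If the cohort was never opened, the effect is zero.

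The confirmatory analyses of PFS, ORR and OS use the FAS, so these patients do not enter them. The PPS definition is ambiguous and should be tightened, but it is not shown to admit these patients. This is a cheap improvement to the safety reporting and does not threaten the trial's main conclusions.

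**What to change.** - **SAP 5.2.3 and 8:** keep the all-treated SAF for overall safety reporting. Base the between-arm safety tables on randomised and treated patients. Show directly allocated Sub-study C patients in a separate column, and add a pooled all-PRRT column.
- **SAP 5.2.2:** define the PPS as FAS patients without a serious protocol deviation.
- If the cohort was never activated, one sentence in the SAP saying so settles the safety-table part.

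The cost is a few lines of SAP text and one or two extra table columns. The comparative PRRT safety column would hold up to 20 fewer patients, all of whom are still fully reported in the other columns.

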5.2.4 Other Populations

In case of specific assessments in specific groups of patients, analyses will only be conducted in the appropriate group of patients where relevant. As an example, the analysis of sub-study variables will only be analysed based on the population of patients who actually participated in the corresponding sub-study.

5.3 General Statistical Methods

Statistical analyses will be performed after the data base was appropriately locked.

All data from the CRF and other study and measurement documents will be analysed. Continuous parameters will be summarised using descriptive statistics (number, mean, standard deviation, minimum, median, maximum) and categorical parameters using frequency tables. Corresponding 95% confidence intervals will be presented additionally where meaningful.

Statistical hypothesis testing of the primary variable and the key secondary variables will be performed maintaining an overall type I error (alpha) of 5% (two-sided).

Multiplicity will be accounted for by adhering strictly to the described interim analysis and hierarchy testing plan with regard to the primary and the key secondary endpoints (see Section 5.7).

Exploratory statistical hypothesis tests will be used at a significance level of 0.05 (two-sided) considered at a purely descriptive level.

Withdrawals and protocol deviations will be listed. Missing data that cannot be obtained will not be substituted, unless stated otherwise (See Section 5.5). A given data set entry is presumed to be an outlier if the value is evidently contrary to generally accepted data. Such occurrences will be recorded. Results from analyses excluding outliers may be explored by comparing results based on the complete data set, differences will be discussed.

5.4 Covariates and Subgroups

To enable a meaningful subgroup analysis randomisation will be stratified for primary tumour origin with a sufficient number of

- GE-NETs and
- P-NETs

Furthermore, a sufficient number of

- Treatment-naïve patients (1st line) and
- patients with previous therapies (2nd line)

must be enrolled to allow conclusions on efficacy in each of the sub-populations.

5.4.1 Primary Tumour Origin (GE-NET vs. P-NET)

In this trial patients with histologically and clinically confirmed diagnosis of well-differentiated neuro-endocrine tumour of

- non-functional gastroenteric origin (GE-NET) or
- functional or non-functional pancreatic origin (P-NET)

will be eligible.

Therefore, stratified randomisation will be used to ensure a balanced frequency of GE-NET and P-NET patients in both treatment arms. Inclusion of an equal number of GE-NET and P-NET will be attempted, but any ratio will also be acceptable as long as it allows meaningful subgroup analysis.

5.4.2 Prior Medical Treatment (1st line vs. 2nd line)

In the present trial both,

- treatment naive (1st line), and
- patients having progressed under prior medical therapy (2nd line)

will be eligible.

Since prior medical treatment status is expected to be a relevant baseline co-variate, stratified randomisation will be used, to ensure a balanced frequency of 1st line and 2nd line subjects in both treatment arms.

In addition, the evaluation of prior medical treatment in 2nd line patients will be differentiated into chemotherapy, SSA, targeted therapy (e.g. sunitinib), and others.

5.4.3 Tumour grade (G1 vs. G2), KI-67 and KPS/ECOG

Tumour grade, KI-67, and baseline clinical status, determined using the KPS/ECOG are suspected to be further relevant baseline co-variables, which should be investigated at the time of analysis.

5.4.4 Other Characteristics

Summary tables and/or listings will be provided for demographics and other baseline characteristics, including the above-mentioned variables and:

- Age, ethnic origin, sex, physical exam
- Medical/surgical history at baseline,
- Prior and concomitant medication
- Time from primary diagnosis, time from diagnosis of progression, number and type of prior therapies for condition, site(s) of metastases
- Histological entity, functional state
- HRQL scores at baseline (QLQ C30 and GI.NET21 questionnaires)
- Change of inclusion criteria (protocol version 2.2 amendment 2) based on record in CRF.

All variables of population characteristics will be confirmed by non-parametric statistical testing for both treatment groups to check their comparability at baseline (except for detailed physical examination, medications, and medical/surgical history). If there should be major differences between the treatment groups, their impact on the analysis will be investigated including with stratified methods if appropriate.

In addition, appropriate methods (stratification, multivariate analyses, subgroup analyses) will be used to assess the impact of patient characteristics, tumour histology and rescue SSA drugs on tumour response as foreseen in the exploratory study objectives.

Cox proportional hazard model will be used for PFS and OS to explore treatment effect within each subgroup. And forest plots (including p-value and 95 % confidence interval) of hazard ratios for PFS and OS will be presented. The pre-specified subgroups are:

- primary tumour origin (GE-NET vs. P-NET),
- prior medical treatment (1st line vs. 2nd line),
- tumour grade (G1 vs. G2) based on local assessment for baseline
- baseline KPS (70, 80, 90 and 100)
- Received SSA prior to baseline or not
- Received SSA prior to baseline and did not stop prior baseline
- Change of inclusion criteria (protocol version 2.2 amendment 2) based on record in CRF.

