1.1 Preface

^{177}Lu -Edo (^{177}Lu -edotreotide, ^{177}Lu -DOTATOC) is an oligopeptide targeting somatostatin receptors (SSTR) which is over-expressed in certain tumour entities. ^{177}Lu -Edo is used for peptide receptor radiotherapy (PRRT) of patients with metastasised Neuroendocrine Tumours (mNET).

The purpose of the present study is to evaluate efficacy and safety of PRRT with ^{177}Lu -edotreotide in patients with metastatic GEP-NET, in comparison to established medical therapy, using a prospective randomised controlled trial design. Everolimus (Afinitor®) was selected as the comparator. It is a drug licensed for the treatment of unresectable or metastatic, well or moderately differentiated neuroendocrine tumours of pancreatic origin in adults with progressive disease which, more recently, was also approved for the treatment of unresectable or metastatic, well-differentiated (G1 or G2) non-functional neuroendocrine tumours of gastrointestinal origin. Everolimus has an innovative mode of action, high clinical acceptance, and well-documented evidence of efficacy. This study will further be designed to allow a meaningful subgroup analysis of GE-NETs and P-NETs. In addition, by inclusion of both 1st line and 2nd line GEP-NET patients, the issue of optimum timing of PRRT during the disease course will also be addressed by the trial.

Please refer to Section 1 of the current protocol for more details.

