For the sample size calculations, i.e. estimating the sample size, the power and/or the effect size, the following considerations were taken into account:

With regard to PFS, a two-sided logrank test with an overall sample size of $N=242$ subjects (180 events; randomised 1 : 2, $N_1=80$ subjects [68 events] in the everolimus group and $N_2=162$ subjects [112 events] in the ^{177}Lu -edotreotide group) achieves 80% power at a 5% significance level to detect a hazard ratio (HR) of 0.6471 when the everolimus group median survival time is 11 months (i.e., a difference of an additional 6 months in the ^{177}Lu -edotreotide group). The study was planned to last for 48 months of which subject accrual occurs in the first 24 months. The accrual across time is uniform. Of note, the trial sample size was not revised (i.e. decreased) after the protocol amendment that extended the patient follow-up from 24 months to 30 months.

Based on this HR a total sample size of 300 will compensate for a dropout rate (censored data) of 15% for primary endpoint analysis.

With regard to overall response rates, group sample sizes of 200 in the ^{177}Lu -edotreotide group and 100 in the everolimus group achieve 89% power to detect an odds ratio between the group ORRs of 4.2 (that corresponds to rates of 5% and 18%). The proportion in the ^{177}Lu -edotreotide group is assumed to be 5% under the null hypothesis and 18% under the alternative hypothesis. The proportion in the everolimus group is assumed to be 5% according to results of the RADIANT-3 study (Yao et al., 2011). The test statistic used is the two-sided Fisher's Exact Test. The significance level of the test is 5%. A dropout rate of 15% is included in this calculation using PASS software.

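### SAP 5.4.4 plans within-subgroup p-values but no treatment-by-subgroup interaction, although the trial says it will address the timing of PRRT

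*SAP*

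**What the plan says.** SAP 5.4.4 states that a "Cox proportional hazard model will be used for PFS and OS to explore treatment effect within each subgroup", and that "forest plots (including p-value and 95 % confidence interval) of hazard ratios for PFS and OS will be presented". Seven subgroup items are listed for both endpoints, among them tumour origin, line of therapy, grade and KPS in four levels. SAP section 6 adds Cox models that adjust for covariates and an open list of further subgroup factors. Protocol 9.2.3.4 and SAP 5.4.4 also refer in general terms to stratified, multivariate and subgroup methods. Neither document names a treatment-by-factor term, a heterogeneity test or a rule for comparing subgroup hazard ratios.

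On purpose, SAP 1.1 (like Protocol 1.2) says that "the issue of optimum timing of PRRT during the disease course will also be addressed by the trial", because both 1st-line and 2nd-line patients are included. SAP 5.4 (like Protocol 3.1) says that enough patients in each line "must be enrolled to allow conclusions on efficacy in each of the sub-populations".

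On status, SAP 5.3 says: "Exploratory statistical hypothesis tests will be used at a significance level of 0.05 (two-sided) considered at a purely descriptive level". SAP 5.7 treats tests on variables other than PFS, ORR and OS as exploratory, and SAP section 7 calls p < 0.05 significant only descriptively.

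**The concern.** Whether PRRT is better placed in 1st or 2nd line depends on whether its effect relative to everolimus differs between the two. That is a contrast between two hazard ratios. A p-value within each line tests each hazard ratio against 1 and says nothing direct about their difference. If one line gives p < 0.05 and the other does not, a reader may infer that the effect depends on line, although this pattern arises easily when the effect is the same in both. At stake is a misleading statement on treatment timing, or on any of the other listed factors, drawn from a display that carries no measure of the difference.

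**Working it through.** **Inputs.** SAP section 4 gives the PFS design: "180 events; randomised 1 : 2", with 68 everolimus and 112 <sup>177</sup>Lu-edotreotide events. It "achieves 80% power at a 5% significance level to detect a hazard ratio (HR) of 0.6471". SAP Table 2 calls this effect (17 vs 11 months) the minimal clinically relevant difference. It lists 22 vs 11 months (HR 0.50) as the expected effect and 30 vs 11 months (HR 0.3667) as the historical effect. The exploratory test level is two-sided 5% (SAP 5.3). Protocol 3.1 aims ideally for 150 GE-NET and 150 P-NET patients. No split is given for line of therapy.

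**Reproducing the plan's figure.** Schoenfeld power is Φ(√(d × 1/3 × 2/3) × |ln HR| − 1.96), where d is the number of events.
- With d = 180 and HR 0.6471: √40 × 0.435 − 1.96 = 0.79, so power is 78.6%.
- With the SAP's own event split, the variance is 1/68 + 1/112 = 0.0236, and power is 80.8%.

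Both agree with the stated 80%, so the formula is suitable for the subgroup step.

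**Two subgroups, one common true HR.** Assume independent subgroups and events in proportion to subgroup size. With powers p1 and p2, the chance that exactly one is significant is p1(1 − p2) + p2(1 − p1). For 90 events per half, √(90 × 2/9) = 4.472. At HR 11/17, 4.472 × 0.435 − 1.96 = −0.013, so p = 49.5%, and 2 × 0.495 × 0.505 = 50%.

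| True HR in both subgroups | Power per half (90 events) | Exactly one significant, 50:50 | Exactly one significant, 70:30 (assumed) |
|---|---|---|---|
| 0.6471 (minimal) | 49.5% | 50% | 55% |
| 0.50 (expected) | 87.3% | 22% | 34% |
| 0.3667 (historical) | 99.4% | 1.1% | 6.5% |

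At HR 0.647 with an assumed 60/120 split, the powers are 35.6% and 61.3%, and 0.356 × 0.387 + 0.613 × 0.644 = 53%.

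If PFS were read at the first planned look (90 events, equal split), the three rates would be 40%, 48% and 20%. For OS (198 events, HR 0.66, equal halves) the rate is 50%.

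**What an interaction test does instead.** By construction it flags a difference in 5% of trials per factor when the effect is uniform. In simulation at HR 0.6471 with 90/90 events, it was non-significant in about 90% of the trials where the two p-values disagreed.

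Its limitation is power. The variance of the difference in log hazard ratios is 1/20 + 1/20 = 0.10, so the standard error is 0.316. The ratio of hazard ratios detectable with 80% power is exp((1.96 + 0.842) × 0.316) = 2.43. Power is 59% for a ratio of 2.0 and 25% for 1.5.

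**The case against.** The strongest reply is that the SAP labels these analyses exploratory and descriptive, keeps them outside the confirmatory hierarchy and prints confidence intervals beside the p-values. That stands: the confirmatory type I error is untouched, and a careful reader would see the intervals overlap. It does not supply an analysis for the timing question, and a display marking one subgroup significant and the other not invites the wrong comparison.

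A second reply is that the documents promise less than they seem to. A reader might infer that they commit to comparative conclusions for GE-NET against P-NET as well as for line of therapy. They do not. The statement in SAP 5.4 about conclusions in each sub-population concerns efficacy within each line, which a subgroup hazard ratio with its interval can address. For tumour origin the texts ask only for a meaningful subgroup analysis. Only the timing remark is comparative, and it stands in the rationale and preface, not among the objectives.

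Third, the SAP does not say outright that the Cox models are fitted separately, and table specifications sit in a separate tracker that is not available here. What the text supports is that no interaction is specified, not that none will ever be run.

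Fourth, HR 0.647 is the SAP's minimal effect, not its expected one. This is correct, and the range in the working reflects it.

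**Conclusion.** The concern holds as a gap in an exploratory analysis. SAP 5.4.4 specifies within-subgroup estimates and p-values but no estimate or test of whether the effect differs, while both documents say that the timing of PRRT will be addressed.

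Under a uniform effect with 180 events and an equal split, exactly one of two subgroups is significant in about 50% of trials at HR 0.647, 22% at HR 0.50 and 1% at HR 0.3667. A reader might infer from the first figure that false contrasts will be common whatever the truth. The documents do not support that, because at the historical effect they are rare at 180 events. Nor do they support reading this as a threat to the trial's confirmatory claims.

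The figures rest on Schoenfeld variances at 2:1 allocation, independent subgroups and events in proportion to subgroup size. The equal split is a stated aim for tumour origin only. For line of therapy it is an assumption, as are the 60/120 and 70:30 splits.

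**What to change.** Amend SAP 5.4.4 as follows.

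- For each pre-specified factor, and for PFS and OS, fit one Cox model on the FAS with treatment, factor and treatment-by-factor terms, stratified by the randomisation factors. Where the factor is itself a stratifier (tumour origin, line of therapy), the strata absorb its main effect, and only treatment and the interaction are estimated.
- For four-level KPS, name in advance either a global interaction test or a trend test. State the comparison group for the item on SSA continued past baseline, which is listed without one.
- On the forest plot, show subgroup hazard ratios with 95% CIs, the ratio of hazard ratios with its 95% CI, and the interaction p-value. Remove the within-subgroup p-values.
- State that differences between subgroups are judged only from the interaction estimate. Removing the p-values is not enough, because an interval that excludes 1 in one subgroup and includes it in the other shows the same contrast.
- State that a non-significant interaction is not evidence of homogeneity, given 80% power only for a ratio of about 2.4 with 90/90 events.

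The cost is SAP wording and one model per factor and endpoint (7 × 2 = 14). Design, sample size and data collection do not change.
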